## **STUDY PROTOCOL AND STATISTICAL ANALYSIS PLAN**

**1. Title of the Study:** The Effect of Acupressure on Fatigue, Quality of Life and Comfort in Hemodialysis Patients. Randomized Controlled Study

**2. Purpose of the Study:** In this study, it was aimed to determine the effect of acupressure on fatigue, quality of life and comfort in hemodialysis patients. In our research, it is aimed to reduce fatigue, increase the quality of life and comfort level in hemodialysis patients with acupressure applied.

**3. Rationale for the Study:** Literature was associated acupressure with fatigue (1-10), pain (11), pruritus (12), sleep problems (4,13-17), depression (7,8,18), in hemodialysis patients and chronic kidney disease patients. It has been reported acupressure to be effective in controlling many symptoms such as nausea-vomiting, muscle cramps (19) and itching (20). In the literature, it is noted that acupressure has a positive effect on the fatigue symptoms of hemodialysis patients. Studies have shown that hemodialysis patients experience high levels of fatigue, and fatigue is the most common factor in patients with CKD, significantly affecting their daily living activities and quality of life (1,2,5,20-22).

Studies on fatigue, quality of life and comfort of acupressure in hemodialysis patients are limited in the literature. However, there is no study in the literature examining the effects of acupressure on fatigue, quality of life and comfort in hemodialysis patients. High-quality, randomized controlled studies with sufficient sample size are needed to demonstrate the effect of acupressure in hemodialysis patients. There is no other randomized controlled study examining the effects of acupressure application on fatigue, quality of life and comfort in hemodialysis patients planned to be included in our study.

Therefore, in this study, it was aimed to draw attention to the importance of acupressure by revealing the effect of acupressure on comfort and quality of life in individuals who experience fatigue due to hemodialysis. It is thought that independent nursing initiatives will be supported with acupressure to be applied in the research, and it will contribute to the practices of nurses. In addition, the adoption of the results of our research by hospital administrations as an institutional policy will guide the care of nurses.

### **4. Research Materials and Methods:**

The study is planned as a prospective, single-blind randomized controlled randomized study to determine the effect of acupressure on fatigue, quality of life and comfort in hemodialysis patients. This randomized controlled trial will be reported according to CONSORT guidelines and registered on ClinicalTrials.gov (23).

Patients who receive hemodialysis treatment in Adana City Hospital dialysis unit, volunteer to participate in the study and meet the research criteria, will be assigned to the study and control groups according to the days they come for dialysis treatment by lottery method (coin toss). Heads will be determined as the working group and heads will be determined as the control group. Randomization in the study will be done on the website of randomizer.org and patients will be included in the study and control groups with the appropriate randomization method according to the dialysis unit list (12,24).

**NCT Number:** 05892679

The Effect of Acupressure on Fatigue, Quality of Life and Comfort in Hemodialysis Patients. Randomized Controlled Study

The data obtained from the research will be evaluated using appropriate statistical methods. In the analysis of comparative data, parametric or nonparametric tests will be used by evaluating the conformity to the normal distribution. A package program will be used in the statistical analysis of the research.

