#### **4.1. Statistical analysis**

Demographic and patient-reported results in the study will be summarized with descriptive statistics. Continuous, normality checks of measurements will be tested with the Shapiro Wilk test. Differences in repeated measures between groups will be tested with the Repeated Measures test (repeated measure analysis of variance). Bonferroni test will be used for pairwise comparisons. Differences between groups for each measurement will be tested with the Independent Samples t-test. Number and percentage values will be given as descriptive statistics. Pearson chi-square and Fisher Exact chi-square tests will be used for differences between categorical variables. Number and percentage values will be given as descriptive statistics. P<0.05 will be taken as statistical significance.

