**Output:**

Noncentrality parameter <math>\lambda</math>	= 14.000000
Critical F	= 4.0847457
Numerator df	= 1.000000
Denominator df	= 40.000000
Total sample size	= 42
Actual power	= 0.9545279

In the study, 60 hemodialysis patients were randomly assigned to the study and control groups. The study group (n=30) Acupressure is formulated according to the standards of the World Health

[figure not shown]
**NCT Number:** 05892679

Organization and in a certain order to the points of Stomach 36 (St 36), Gall Bladder 34 point (GB 34), Spleen 6 point (SP 6) and Kidney 1 point (K 1) will be applied. Consideration will be given to the appropriate pressure intensity and duration. Since the reactions of individuals will be different from each other, the stiffness and pressure will be adjusted according to the sensitivity of the individual in order not to cause tissue damage. Pressures will be applied manually by a single practitioner. Considering the anatomical area where the point is located, the most suitable thumb, index and/or middle finger will be used for application to the relevant point. Successive compressions will be applied at a frequency that does not disturb the patient, does not cause pain, and has a calming effect.

Considering the studies done, a person will be given acupressure three times a week for four weeks. No intervention will be made to the control group (n=30). In order to avoid ethical problems both groups will be given an informative training on acupressure and fatigue, increase the quality of life and comfort level in hemodialysis patients at the end of the study. The primary outcome of the study is the effect of acupuncture on fatigue in hemodialysis patients. The secondary result of the study is the effect of acupuncture on quality of life and comfort level in hemodialysis patients.

[figure not shown]
[figure not shown]
The results will be collected before the acupressure and in the 4th week of the last intervention.

Table 1. Application Points Used in the Study (33)

Application Site Name	Picture of Application Site	Description of Application Site
Stomach 36. point  (Zusanli: ST 36)		In the leg, it is one finger width lateral to the anterior crest of the tibia, and 3 cuns below the ST 35 in the depression on the lateral side of the patella.

**NCT Number:** 05892679

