## 5. Research Flow Process

The Flow Chart of this research will be completed in three stages and four steps as indicated in Figure 1.

**First Stage (Preparatory Stage):** An internationally approved acupressure certificate was obtained by the researcher in July 2022 (the certificate is in Annex I). The place where the acupressure application will be made will be arranged in accordance with the acupressure application. Necessary materials will be purchased for acupressure application (bed cover, pillow, etc.)

**Second Stage (Implementation Stage):** This stage will consist of four steps.

**In the first step:** In the first step of the application, patients who receive hemodialysis treatment in Adana City Hospital dialysis unit and meet the research criteria and are willing to participate in the research will be given brief information about the research and their verbal consent will be obtained. The fatigue experience VAS scores of the patients who accepted to participate in the study on a voluntary basis will be calculated. Those with a VAS value of fatigue severity  $\geq 4.0$  between 0 and 10 points will constitute the sample of the study.

**In the second step:** Sample selection will be completed in accordance with the inclusion, exclusion and exclusion criteria of the study, and then randomization will be performed. The patients will be informed about the purpose of the research and the research process, and the patients will be asked to fill in the "Piper Fatigue Scale", "Kidney Disease and Quality of Life Form" and "Hemodialysis Comfort Scale" as a pre-test with an informed consent form.

**Third step:** Patients in the study group will be given a total of 12 sessions of acupressure application bilaterally to Stomach 36 (St36), Gall Bladder 34 (GB34), Spleen 6 (SP6) and Kidney 1 (K1) acupuncture points for 4 weeks and 3 days a week for 20 minutes. No intervention will be made to the control group other than routine maintenance during the four-week period.

**Fourth step:** After the 4-week acupressure process is over, after the last acupressure session, the patients in the study group will have the "Piper Fatigue Scale", "Kidney Disease and Quality of Life Form" and "Hemodialysis Comfort Scale" filled face-to-face as a post-test. At the end of 4 weeks, the control group will have to fill in the "Piper Fatigue Scale", "Kidney Disease and Quality of Life Form" and "Hemodialysis Comfort Scale" as a post-test before hemodialysis.

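### The trial is labelled single-blind without naming a blinded party, and the design leaves patients, who rate all outcomes themselves, and the practitioner aware of the arm

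*Combined protocol and SAP*

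**What the plan says.** The only statement on blinding is the label in section 4, Research Materials and Methods: "prospective, single-blind randomized controlled randomized study". The party meant is not named. No sham or attention control, blinded data collector or blinded analyst is described anywhere.

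The arms are described as follows:

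- **Study group.** Section 5, Research Flow Process (third step) gives 12 sessions of 20 minutes, three days a week for four weeks. The intervention text in section 4.3 adds: "Pressures will be applied manually by a single practitioner".
- **Control group.** Section 5, third step: "No intervention will be made to the control group other than routine maintenance during the four-week period".
- **Patient information.** Section 5, second step: "The patients will be informed about the purpose of the research and the research process".

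On outcomes, section 4.3 states: "The primary outcome of the study is the effect of acupuncture on fatigue in hemodialysis patients". (The wording there is acupuncture, although the intervention is acupressure.) The only fatigue instrument given at both pre-test and post-test is the Piper Fatigue Scale, which patients fill in. The quality-of-life and comfort scales are also filled in by patients. Section 4.1 refers to the results as patient-reported: "Demographic and patient-reported results in the study will be summarized with descriptive statistics".

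For the post-test, section 5 (fourth step) has the study group's forms "filled face-to-face as a post-test" after the last acupressure session. The control group completes them at the end of four weeks, before hemodialysis. Figure 1 places the control forms at the end of an interview.

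**The concern.** A reader of the report will take single-blind to mean that someone whose knowledge of the arm could affect the fatigue score did not have that knowledge. Nothing in the plan supports this. A study patient has had 12 × 20 = 240 minutes, or 4 hours, of hands-on contact; a control patient has had none. Each knows which arm they are in when answering the questionnaire. A difference in favour of acupressure could therefore reflect expectation, courtesy or contact time, and the plan would report it as the effect of acupressure. Section 3 hopes that hospital administrations will adopt the results as policy, so the label will influence how far the result is trusted.

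The differing post-test occasion adds a second arm-dependent influence. One group answers after a treatment session and the other before dialysis, so state at the time of answering may differ for reasons unrelated to a lasting effect.

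**Working it through.** **Who could be blinded, and would it help?**

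| Party | What the plan describes | Aware of arm? |
|---|---|---|
| Patient | 12 manual sessions versus routine care; told the purpose and process | Yes, by design |
| Practitioner | One person applies all pressure by hand | Yes |
| Outcome assessor | The patient, by questionnaire | Yes, same person |
| Data collector | Not described | Unknown; the answers still come from an unblinded patient |
| Analyst | Not described | Unknown; acts after the answers are given |

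**The plan's own sample-size figure (section 4.3).** Inputs: f = 0.5, N = 42, m = 2 measurements, correlation ρ = 0.5, between-factor test, α = 0.05.

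λ = f²·N·m / (1 + (m − 1)ρ) = 0.25 × 42 × 2 / 1.5 = 14.0, with df 1 and 40. The critical F is 4.0847 and the power 0.9545. Both match the printed output, so the sizing arithmetic is reproduced and this point does not affect it.

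**Illustration of a reporting bias.** Assumptions: no true effect; n = 30 per arm; SD 1 at each measurement; ρ = 0.5; a shift of b SD in the study group at post-test only; two-sided 0.05; noncentral t with 58 df. The range of b is assumed, because the documents give none.

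- Post-test t-test (section 4.1): noncentrality = b / √(2/30) = b / 0.2582.
- Group-by-time test: the SD of change is √(2(1 − 0.5)) = 1, so the noncentrality is the same.
- Between-factor test (used for sizing): the shift in the two-measurement mean is b/2, and the SD of that mean is √((1 + 0.5)/2) = √0.75 = 0.866. Noncentrality = (b/2) / (0.866 × 0.2582) = (b/2) / 0.2236.

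| Assumed bias b (SD) | Noncentrality, post-test t | P(p<0.05) | Noncentrality, between-factor | P(p<0.05) |
|---|---|---|---|---|
| 0.2 | 0.775 | 0.119 | 0.447 | 0.072 |
| 0.3 | 1.162 | 0.208 | 0.671 | 0.101 |
| 0.4 | 1.549 | 0.332 | 0.894 | 0.142 |
| 0.5 | 1.936 | 0.478 | 1.118 | 0.196 |

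The nominal rate is 0.05. With two equal groups, f = 0.5 is a difference of 2 × 0.5 = 1.0 SD in the average of the two measurements. A 0.3 SD bias at post-test alone shifts that average by 0.15 SD, or 15% of the planned effect. A larger sample would not remove the bias.

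Section 5 (second step) lists randomization before the pre-test, so the assumption that bias enters only at post-test is a simplification.

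**The case against.** The strongest defence is that the label is undefined rather than shown to be false. The plan does not exclude a blinded data collector or analyst, and awareness among patients and the practitioner is inferred from the design, not written. That is correct as to wording. It does not rescue the fatigue result, because the bias arises when an unblinded patient answers.

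A second defence is that the comparator is openly routine care, and the plan claims no superiority over sham. This also stands: such a comparison is legitimate if it is described as what it is.

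Four stronger readings are tempting and are not supported:

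- A reader might infer that the plan claims protection against expectation bias. No section mentions it; the label only implies some protection.
- A reader might infer that the mode of collection differs by arm, since only the study group's post-test is called face-to-face. Figure 1 mentions an interview for controls, so only a difference in occasion is documented.
- A reader might infer that the practitioner collects the forms. Section 5 says that the researcher holds the acupressure certificate, but no section says who hands out or collects the questionnaires.
- A reader might compute the illustration with ANCOVA, which gives 14%, 26%, 42% and 59% for the same biases, or set a 0.3 SD bias directly against 1.0 SD and call it 30% of the planned effect. ANCOVA is not in section 4.1, and the sizing effect is an average over both measurements, so neither figure describes this plan.

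**Conclusion.** The point holds as one of labelling, collection procedure and interpretation. The single-blind label names no blinded party, and the design leaves patients (who are the outcome assessors) and the practitioner aware of the arm. The label therefore gives the fatigue result no protection. The post-test occasion is also described differently by arm.

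The size is illustrative only. Under assumed post-test biases of 0.2, 0.3, 0.4 and 0.5 SD with no true effect, false-positive rates are about 12%, 21%, 33% and 48% for the planned post-test t-test (and for group-by-time at correlation 0.5), and 7%, 10%, 14% and 20% for the between-factor test. These figures rest on 30 analysed patients per arm and on bias entering only at post-test. Whether any such bias occurs, and how large it is, cannot be known from the documents. The trial remains interpretable as an open comparison with routine care.

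**What to change.** 1. In section 4, replace the single-blind label with *open-label for patients and practitioner*. If item 3 is adopted, add *analyst blinded to coded groups*.
2. In both arms and at both time points, collect the three questionnaires on the same occasion relative to the dialysis session and in the same way: self-completed, returned sealed, and without the acupressure practitioner present. Bring section 5 (fourth step) and Figure 1 into line with this.
3. Give the analyst groups coded A and B until the primary analysis is fixed.
4. State the conclusion as acupressure sessions, including practitioner contact, versus routine care, and list patients' awareness of their arm as a limitation.

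The cost is protocol wording, an envelope procedure and some reading help from existing unit staff; no extra patients or visits are needed. The label and the claim become less favourable. Items 2 and 3 limit courtesy, setting and analyst effects, but patients still know their arm, so expectation bias is reduced at best. If data have already been collected, items 1 and 4 can still be adopted, as can item 3 if the analysis has not begun.

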#### **4.2. Research Design: Prospective**

#### **4.3. Design of the Research**

The population of the research will be hemodialysis patients treated at Adana City Hospital between 30 May 2023 and 30 September 2023. The research sample will consist of patients who meet the research criteria and agree to participate voluntarily in the research. The sample number of the study was calculated using the G\*Power 3.1.9.7 program (25). In the calculation, a sample calculation was made for repeated measures ANOVA test. In the calculation, Cohen's medium effect size ( $f = 0.5$ ), 5% margin of error ( $\alpha = 0.05$ ) and 95% power ( $1-\beta = 0.95$ ) and the correlation value between repeated measurements were taken as 0.50 for each group (study and control). ) sample size was calculated as 21 patients (42 patients in total). Considering the possibility of patients leaving the groups during the research process, the number of samples for each group was increased by 30%, taking into account the possibility of data loss in order not to adversely affect the statistical power, and 30 patients (total of 60 patients) for each group (study and control) were included in the sample planned (26). Randomization in the study will be done on the website of randomizer.org and patients will be included in the study and control groups with the appropriate randomization method according to the dialysis unit list (27).

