#### **F tests - ANOVA: Repeated measures, between factors**

**Analysis: A priori: Compute required sample size**

**Input:**

Effect size f	= 0.5
<math>\alpha</math> err prob	= 0.05
Power (1-<math>\beta</math> err prob)	= 0.95
Number of groups	= 2
Number of measurements	= 2
Corr among rep measures	= 0.5

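### Two allocation methods are stated and not reconciled, the unit of randomisation is not defined, and one reading would tie treatment to dialysis day

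*Combined protocol and SAP*

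**What the plan says.** The combined protocol and SAP describes allocation in several places.

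- Section 4 (Research Materials and Methods) says that eligible volunteers "will be assigned to the study and control groups according to the days they come for dialysis treatment by lottery method (coin toss"). The coin rule follows: "Heads will be determined as the working group and heads will be determined as the control group". The same face is printed for both arms, probably a slip.
- The same paragraph then gives a second method, a draw on randomizer.org using the dialysis unit list. Section 4.3 repeats this one alone: "Randomization in the study will be done on the website of randomizer.org and patients will be included in the study and control groups". The type of randomisation is described only as appropriate.
- After the sample size output, the text uses the past tense: "In the study, 60 hemodialysis patients were randomly assigned to the study and control groups".
- Section 4.1 plans patient-level tests with no term for dialysis day: a repeated measures ANOVA and "Differences between groups for each measurement will be tested with the Independent Samples t-test". The sizing is for "ANOVA: Repeated measures, between factors".
- On timing, section 5 (Research Flow Process) says that in the first step patients "will be given brief information about the research and their verbal consent will be obtained", and fatigue is screened by VAS. Step two of that section reads: "Sample selection will be completed in accordance with the inclusion, exclusion and exclusion criteria of the study, and then randomization will be performed". Listed after that are the informed consent form and the pre-test, including the Piper Fatigue Scale. Figure 1 gives the same order.

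**The concern.** The unit of randomisation decides whether the planned analysis is valid, and the text does not define it. If patients are randomised, the tests in section 4.1 and the sizing are of the right kind. If whole dialysis-day groups are tossed, every patient in an arm shares a day. Treatment is then confounded with anything else that differs between days, and patients within an arm are not independent. With one day group per arm, a larger sample does not cure this. The text as it stands also does not allow the allocation to be described as the CONSORT reporting promised in section 4 would require.

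A separate, smaller matter is the order of steps. Fatigue is the primary outcome and the Piper scale is self-rated. If a patient knows the arm when filling in the pre-test, that knowledge can affect the baseline. The trial is called single-blind, but the plan does not say who is blinded. Willingness to take part and VAS eligibility are settled before randomisation, so this matter is limited to the signed consent form and the pre-test.

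**Working it through.** **1. The plan's own sample size.** Inputs from section 4.3 and the printed output: f = 0.5, alpha = 0.05, 2 groups, m = 2 measurements, correlation 0.5, N = 42.

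lambda = f² × N × m / (1 + (m − 1) × 0.5) = 0.25 × 42 × 2 / 1.5 = 14.0. With df (1, 40), the critical F is 4.0847 and the power 0.9545. All match the output. The denominator df of 40 is 42 patients minus 2 groups, so the calculation takes patients as independent units. Allowing for 30% loss, 21 / (1 − 0.30) = 30 per arm, as planned. The arithmetic is right for individual randomisation.

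**2. Readings that the text allows.**

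| Reading | Arm tied to day? |
|---|---|
| randomizer.org allocates individual patients; the coin sentence is a leftover | No |
| randomizer.org forms two sets of patients and a coin labels them | No |
| Patients are randomised within each dialysis day | No |
| The coin assigns day groups to arms, with or without randomizer.org picking patients within them | Yes |

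A separate toss for each patient is also conceivable, but it would not by itself deliver the fixed 30 and 30: the chance of an exact 30/30 split in 60 independent tosses is C(60,30)/2^60 = 0.103.

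**3. Consequence of the last reading.** This is an illustration. The documents give neither the number of day groups nor an intraclass correlation (ICC), so both are assumed. Take n = 30 per arm, one day group per arm and a day effect that is stable over the 4 weeks. The critical value is t with 58 df = 2.0017.

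- Post-test t-test: type I error = 2 × P(t58 > 2.0017 / sqrt(1 + 30 × ICC/(1 − ICC))). At ICC 0.01, 30 × 0.01/0.99 = 0.303, sqrt(1.303) = 1.1415 and 2.0017/1.1415 = 1.754, which gives 0.0848.
- Between-groups effect averaged over both measurements, as sized: the within-day variance is (1 + 0.5)/2 = 0.75 times (1 − ICC), so type I error = 2 × P(t58 > 2.0017 / sqrt(1 + 30 × ICC/(0.75 × (1 − ICC)))).
- More than one day group per arm: simulation of the post-test t-test, 100,000 runs per setting.

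| Type I error at nominal 5% | ICC 0.01 | ICC 0.02 | ICC 0.05 |
|---|---|---|---|
| Post-test, one day group of 30 per arm | 8.5% | 12.0% | 21.8% |
| Average of pre and post, one of 30 per arm | 9.7% | 14.3% | 26.1% |
| Post-test, two of 15 per arm | 6.7% | 8.4% | 13.6% |
| Post-test, three of 10 per arm | 6.0% | 7.2% | 10.4% |

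At ICC 0.001 with one day group per arm, the post-test figure is 5.3%. A stable day effect cancels from the change score, and in the simulation the group-by-time test stayed between 4.9% and 5.1% in all settings. It would not cancel if day groups also changed differently over the 4 weeks.

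**4. Analysis by day group.** With two or three day groups per arm, a t-test on day-group means has 2 or 4 df. The critical t is then 4.30 or 2.78, against 2.00 for 58 df. With one per arm there are no degrees of freedom left to separate treatment from day.

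**The case against.** The strongest reply is that the text leans towards patients as the unit. The randomizer.org sentences speak of placing patients in groups, the statement after the sample size output does too, randomisation follows patient-level sample selection, and the sizing and tests are at patient level. The day reading rests on one phrase beside a visibly garbled coin rule. That phrase may mean only randomisation within each day, which would be sound. All of this stands, and for that reason the point is an unresolved contradiction and not a demonstrated bias.

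A reader might infer that treatment is confounded with dialysis day in this trial, or that 42 is the wrong sample size. The documents support neither: no passage says whole day groups were tossed, and the sizing reproduces for individual randomisation. A reader might also infer that patients know their arm at the pre-test. The plan does not say that the arm is disclosed by then, only that these forms come after randomisation, with no mention of concealment.

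It is also fair that the inflation figures rest wholly on assumed values, that they vanish under individual randomisation, and that a stable day effect leaves the group-by-time test intact. That test is only partial protection, because section 4.1 does not say which effect of the repeated measures ANOVA answers the primary question, and the sizing is for the between-groups effect.

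What the reply does not do is remove the sentence that allocates by day. If that sentence is followed for whole day groups, no later analysis can repair a design with one group per arm.

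**Conclusion.** The point holds as an internal inconsistency that must be resolved. Two allocation methods are stated, nothing reconciles them, and the unit of randomisation is suggested but not defined. There is high confidence in the ambiguity and none claimed for actual confounding.

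The size depends on the answer. If patients were randomised individually, or within day, there is no inflation of this kind and the sizing stands. If whole day groups were the unit, with one per arm, 30 patients each, a stable day effect and an assumed ICC of 0.01 to 0.05, the post-test t-test runs at 8.5% to 22% in place of 5%, and treatment cannot be separated from day at any sample size.

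The order of consent form, pre-test and randomisation is a separate matter that does not depend on which method was used. It is conditional on the arm being known when those forms are completed.

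**What to change.** **If allocation has not happened:**

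- Replace the coin-toss and day sentences in section 4 with one method: individual 1:1 randomisation of the eligible patients by randomizer.org, as in section 4.3. Name the patient as the unit. Because sample selection is completed first, one fixed draw giving 30 and 30 is enough.
- If the day phrase meant randomisation within each dialysis day, say so, give a rule for odd-sized day groups that keeps 30/30 overall, and include day group as a factor in the model. Otherwise stratifying by day is optional.
- Complete the informed consent form and the pre-test before the arm is generated or revealed, and align section 5 and Figure 1 with this. State who is blinded.

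The cost is wording and a change in the order of two steps. One downside is that arms sharing dialysis days may let control patients see the intervention, which could dilute the contrast.

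**If allocation has already happened**, as the past tense after the sample size output may indicate, report what was actually done:

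- If patients were allocated individually, correct the text. A sentence or two is enough.
- If day groups were allocated, say so and do not describe the trial as individually randomised. With one group per arm, state that treatment and day effects cannot be separated. With several, analyse at day-group level and accept the loss of precision: with two or three per arm, only 2 or 4 df.
- If the consent form or pre-test was completed after the arm was known, report that as a limitation of the baseline.

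### The plan leaves the test for fatigue to a normality check that has no trigger or fallback; fixing one baseline-adjusted ANCOVA would settle this and gain about 8 to 11 points of power

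*Combined protocol and SAP*

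**What the plan says.** Two parts of the combined protocol and SAP deal with the choice of test.

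- **Section 4 (Research Materials and Methods)** states a general rule: "parametric or nonparametric tests will be used by evaluating the conformity to the normal distribution".
- **Section 4.1 (Statistical analysis)** says that "normality checks of measurements will be tested with the Shapiro Wilk test". It then names the tests for continuous scores without any condition: "Differences in repeated measures between groups will be tested with the Repeated Measures test (repeated measure analysis of variance)" and "Differences between groups for each measurement will be tested with the Independent Samples t-test". Bonferroni is used for pairwise comparisons, and chi-square and Fisher tests for categorical variables. The significance rule is "P<0.05 will be taken as statistical significance".

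The outcome statement in section 4.3, after the sample-size output, reads "The primary outcome of the study is the effect of acupuncture on fatigue in hemodialysis patients". It names neither a test nor a contrast. Section 5 has the Piper Fatigue Scale completed as a pre-test and again after four weeks, so a baseline score is available for every patient who starts.

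**The concern.** Section 4 makes the test conditional on the data and section 4.1 does not. For a continuous score, 4.1 names no nonparametric test. It does not give the Shapiro-Wilk significance level, what the check applies to (each arm, each visit, change scores or residuals), or what pattern of rejections would cause a switch. If a switch did occur, the replacement would have to be chosen once the data were in hand, and it would be a test that the sample-size calculation does not cover.

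Even with no switch, 4.1 offers more than one route to a result for fatigue: the effects from a two-group, two-time ANOVA, and a t-test at each time. None is called primary. The routes also differ in how they use the pre-test score, and that affects power more than the choice between a parametric and a rank test does.

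**Working it through.** **1. The plan's own figure.** Inputs from section 4.3 and the G*Power listing: f = 0.5, alpha = 0.05, m = 2 measurements, rho = 0.5, two groups.

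lambda = f² × N × m / (1 + (m − 1) × rho) = 0.25 × 42 × 2 / 1.5 = 14.0. With 1 and 40 df the critical F is 4.0847 and the power 0.9545. N = 40 gives 0.945, so 42 is the smallest even total. The figure reproduces. It is for the between-groups effect of a repeated measures ANOVA.

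**2. How often a switch would occur with normal data.** The plan gives no rule, so this is a range over assumptions. If k independent checks are each made at 0.05 and any rejection switches the test, the chance is 1 − 0.95^k:

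| Assumed rule | Chance of a switch |
|---|---|
| One check (pooled residuals) | 5.0% |
| Two checks (post-test or change, per arm) | 1 − 0.95² = 9.75% |
| Four checks (2 arms × 2 times) | 1 − 0.95⁴ = 18.5% |

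For four checks, 20,000 simulated trials per setting gave 18.5% at 21 per arm and 18.4% at 30 per arm with rho = 0.5, and 16.4% to 19.0% over rho from 0 to 0.9. With Shapiro-Wilk at 0.01 or 0.10 instead, four checks give 3.9% or 34.4%.

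**3. What the switch does.** The assumed rule is any of four rejections leading to a Mann-Whitney test on the post-test.

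- *Type I error*, normal data, post-test comparison: 4.8% at 21 per arm and 5.0% at 30, against 4.8% at both sizes for the t-test alone.
- *Power*, 30 per arm, rho = 0.5, 4,000 trials, switching rule against a fixed ANOVA group-by-time test: 47.0% against 47.4% at 0.5 SD, and 85.4% against 86.3% at 0.8 SD. The loss is at most about 1 point.

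**4. What using the baseline does.** The effects of 0.5 and 0.8 SD are illustrative and not taken from the plan. Take d as the post-test group difference in SD units, n = 30 per arm and r = 0.5. With two times, the ANOVA group-by-time test is a t-test on change. The noncentrality parameters are:

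- post-test t-test: d√(n/2)
- change (group-by-time): d√(n/2) / √(2(1 − r)), where 2(1 − r) = 1
- ANCOVA: d√(n/2) / √(1 − r²), where √0.75 = 0.866

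| d | Test | Noncentrality | Power, noncentral t | Power, simulated (4,000 trials) |
|---|---|---|---|---|
| 0.5 | Post-test t | 0.5 × 3.873 = 1.936 | 47.8% | 48% |
| 0.5 | Group-by-time | 1.936 | 47.8% | 48% |
| 0.5 | ANCOVA | 1.936 / 0.866 = 2.236 | 59.4% | 59% |
| 0.8 | Post-test t | 0.8 × 3.873 = 3.098 | 86.1% | 86% |
| 0.8 | Group-by-time | 3.098 | 86.1% | 85% |
| 0.8 | ANCOVA | 3.098 / 0.866 = 3.578 | 94.0% | 93% |

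Degrees of freedom are 58 for the first two tests and 57 for ANCOVA. The gain is about 11 points at 0.5 SD and 8 at 0.8 SD. If the full 30% allowance for loss were used up (30 × 0.7 = 21 per arm), the same formulas give 35.3% against 44.6% at 0.5 SD and 71.6% against 83.1% at 0.8 SD.

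**5. Where disagreement between tests comes from.** Share of trials with different verdicts, 30 per arm, r = 0.5, normal data:

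| Pair of tests | 0.5 SD | 0.8 SD |
|---|---|---|
| Group-by-time and post-test Mann-Whitney | 33% | 19% |
| Group-by-time and post-test t-test (both named in 4.1) | 33% | 17% |
| Group-by-time and Mann-Whitney on change | 7% | 4% |

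The two parametric tests already in 4.1 disagree about as often as the parametric and rank pair. The assumed rule both switches and changes the verdict in only 5.6% and 3.2% of trials.

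**The case against.** The strongest reply is that section 4 is a general remark and 4.1 the specific plan. Section 4.1 names its tests without condition, and the sample size was computed for repeated measures ANOVA, so 4.1 can fairly be taken to govern. That is a reasonable reading. But both statements stand in the same document, nothing says which prevails, and the Shapiro-Wilk check in 4.1 has no stated purpose unless it feeds the section 4 rule. Taking 4.1 alone would also leave the primary test for fatigue unnamed.

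A reader might infer more than the documents support:

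- **That about one trial in five would switch test.** This needs four checks, each at 0.05, with any single rejection decisive. The plan states none of this, and other readings give 5% or about 10%.
- **That the two branches often reach different verdicts.** The 33% and 19% disagreement depends on a post-test Mann-Whitney fallback that the plan does not name, and it comes from using or ignoring the baseline. A rank test on change scores fits section 4 equally well and disagrees in only 7% and 4%.
- **That false positives rise.** A mechanical rule shows no material rise. If either the group-by-time test or a post-test Mann-Whitney could be picked freely, at least one would be significant in about 8.4% of null trials. That is an upper bound for an unstated choice, and nothing in the plan suggests that such a choice is intended.
- **That switching costs about 10 points of power.** Nearly all of that gap is between ANOVA and ANCOVA, not between switching and not switching.

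It is also fair to say that ANCOVA goes beyond reconciling two sentences. One sentence fixing any single test would cure the inconsistency. ANCOVA is proposed because a primary test has to be named anyway, and it makes better use of data already collected.

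**Conclusion.** The concern holds as a minor point of specification. Sections 4 and 4.1 are not consistent on what decides the test, and the primary analysis of fatigue is not fixed. The possible switch does little harm in itself: it would occur in roughly 5% to 18.5% of trials with normal data and an assumed Shapiro-Wilk level of 0.05, with type I error near 5% and at most about 1 point of power lost.

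The real benefit is in naming one baseline-adjusted analysis, worth about 11 points of power at 0.5 SD and 8 at 0.8 SD. That rests on normal scores, the plan's own correlation of 0.5, 30 patients per arm with complete data, and the ANOVA group-by-time test as comparator. It also takes the Piper score as the fatigue measure, which follows from the data collection steps in section 5 but is not stated with the primary outcome.

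**What to change.** Delete the sentence in section 4 on choosing between parametric and nonparametric tests. In section 4.1, state that:

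- the primary analysis is ANCOVA of the week-4 Piper score on group and pre-test score, whatever the result of any normality test;
- residual plots will be inspected;
- a permutation or rank-based analysis will be reported as a sensitivity analysis;
- the same model will be used for quality of life and comfort;
- any repeated measures ANOVA or per-visit t-test that is kept is supportive only.

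The change should be made before post-test scores are examined. It costs some SAP wording and one sensitivity analysis; recruitment, visits and data collection stay as they are. The downside is some loss against a rank-based approach if scores are strongly skewed. In a log-normal simulation the switching rule had 65.9% power against 60.3% for ANCOVA at 0.5 SD, and 95.2% against 92.2% at 0.8 SD, a difference of 5.6 and 3.0 points. The sensitivity analysis would show whether this matters.
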